4. STATISTICAL ANALYSES

4.1. General Considerations

4.1.1. General Methodology

The ITT Analysis Set will be used for all Study Population analyses and Efficacy analyses, unless otherwise specified. A subset of the ITT analysis set will be used for the primary estimand, excluding participants who did not meet key inclusion/exclusion criteria (see 4.2.2). The Safety Analysis Set will be used for selected Study Population summaries and all safety analyses. The PK analysis Set will be used for all PK analyses. Virology analysis set will be used for all Virology analyses.

In the case of a difference between the stratification assigned at the time of randomization and the data collected in the eCRF, the analyses will be performed based on the data collected in the eCRF, not the assigned stratum at randomization. All analyses will be adjusted for treatment group (sotrovimab 500mg IV, sotrovimab 500mg IM), derived age group (<65 years old, ≥65 years old, see Section 6.2.7), and gender (female, male). Stratification factors of region and vaccination status are not included as covariates due to the small number of non-US and partially/fully vaccinated participants in the ITT analysis set. In addition the 12-17 years old and 18-64 years old categories are combined due to the small number of participants in the 12-17 years old category.

In the case of model convergence issues, if one category dominates within a particular covariate then that covariate may be considered for removal from the model.

Confidence intervals will use two-sided 95% confidence levels unless otherwise specified.

Unless otherwise specified, continuous data will be summarized using descriptive statistics: n, mean, standard deviation (std), median, minimum and maximum. For log-transformed data (e.g. AUC) descriptive statistics will present the geometric mean, standard deviation (SD of log-transformed data) and coefficient of variation. Categorical data will be summarized as the number and percentage of participants in each category.

Efficacy data will be reported according to nominal time of clinical visits unless otherwise stated. Hospitalization status, oxygen supplementation and healthcare resource utilization use will be slotted against the clinical visit date for summaries and analyses by visit.

All data will be reported according to the nominal time of clinic visits and assessments as specified in the protocol unless stated otherwise:

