4.3.1.2. Immunogenicity of VIR-7831

The incidence and titers (if applicable) of serum ADA to VIR-7831 will be listed and summarized for the Week 36 safety summary in the Safety analysis set.

Additional immunologic analyses may be conducted and will be documented in a separate technical document.

4.3.1.3. Progression of COVID-19 by Day 29 (emergency room, hospitalisation for any duration or cause, death)

Progression of COVID-19 through Day 29 as defined by:

1. Visit to a hospital emergency room for management of illness
- OR
2. Hospitalization for acute management of illness for any duration and for any cause
- OR
3. Death

4.3.1.4. Proportion of Participants Who Progress to Develop Severe or Critical Respiratory COVID-19 at Day 8, 15, 22 and 29

Participants are defined as progressing to develop severe respiratory COVID-19 if they require supplemental oxygen either by nasal cannula, face mask, high-flow oxygen devices, or non-invasive ventilation.

Participants are defined as progression to critical respiratory COVID-19 if they require invasive mechanical ventilation or ECMO.

Participants who die prior to the timepoint of interest without first having received supplemental oxygen will be considered to have met the endpoint (composite estimand strategy).

Further detail on the severity of respiratory COVID-19 based on the proportion of participants meeting each tier of the Vir modified version of the NIAID Ordinal Scale for Clinical Improvement (Table 1) will be summarized.

Table 1 Ordinal Scale for Clinical Improvement

Ordinal Scale (Vir modified version, adapted from the Adaptive COVID-19 Treatment Trial [ACTT], 2020; referred to as National Institute of Allergy and Infectious Disease (NIAID) scale hereafter)
1) Not hospitalized, no limitations of activities
2) Not hospitalized, limitation of activities and/or requiring home oxygen ¹
3) Hospitalized, not requiring supplemental oxygen and no longer requiring ongoing medical care (used if hospitalization was extended for infection-control reasons)
4) Hospitalized, not requiring supplemental oxygen but requiring ongoing medical care (COVID-19-related or other medical conditions)
5) Hospitalized, requiring any supplemental oxygen
6) Hospitalized, requiring non-invasive ventilation or use of high-flow oxygen devices
7) Hospitalized, receiving invasive mechanical ventilation or ECMO ²
8) Death

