4.5.5. Oxygen Saturation

Summaries of actual and changes in blood oxygen saturation (SpO₂) will be provided in addition a listing of participants administered oxygen.

Requirement for respiratory support is assessed according to the following categories:

1. Room air
2. Low flow nasal canulae/face mask
3. Non-re-breather mask or high flow nasal cannulae/ non-invasive ventilation (including continuous positive airway pressure support)
4. Mechanical ventilation / extra-corporeal membrane oxygenation
5. Other
6. Death

Changes in requirement for respiratory support (excluding room air) will be summarized using proportions of participants with change from baseline to higher respiratory support in each category by study day using a stacked bar chart.

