6.2.6. Handling of Missing Data

Element	Reporting Detail
General	
 Missing data occurs when any requested data is not provided, leading to blank fields on the collection instrument: 
 These data will be indicated using a “blank” in subject listing displays. Unless all data for a specific visit are missing in which case the data is excluded from the listing. Answers such as “Not applicable”, “Not evaluable” and “Not Done” are not considered to be missing data and should be displayed as such.
Outliers	
 Any subjects excluded from the summaries and/or statistical analyses will be documented along with the reason for exclusion in the clinical study report.
Efficacy Endpoints	
Details around the missing data handling for efficacy endpoints are described in section 6.2.8. In addition:
 
 For the secondary binary endpoint of proportion of subjects who have progression of COVID-19 (i.e., hospitalisation (any duration) OR emergency room visit OR death) through Day 29, missing data will be handled as for the primary endpoint.
Safety Endpoints	
 No missing data imputation will be performed for safety endpoints. Data will be reported as captured.

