	
treatment start date, then set start date= 1st of month.
 
 ▪ Else set start date = study treatment start date. • Else set start date = 1st of month. 
Missing start day and month
 
 • If study treatment start date is missing (i.e. subject did not start study treatment), then set start date = January 1. • Else if study treatment start date is not missing: 
 ◦ If year of start date = year of study treatment start date, then 
 ▪ If stop date contains a full date and stop date is earlier than study treatment start date, then set start date = January 1. ▪ Else set start date = study treatment start date. • Else set start date = January 1.
	Missing end day
	Missing end day and month
	Completely missing start/end date
Oxygen Supplementation	
Completely missing end date
 
If the end date is missing and subsequent record exists and is not missing the start date, impute the missing end date as the start date of the subsequent record.
 
If end date is missing and no subsequent record exists, the method of oxygen supplementation will be considered ongoing at time of database extraction.

Age	Age will be imputed from year of birth. The calculation will use 30 June as the day and month and will calculate the age relative to Screening date.

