6.2.8. Statistical Modelling - Multiple Imputation

Multiple imputation will be used to impute data that is missing following withdrawal of the subject from the study, or following an intercurrent event for hypothetical estimands (if applicable), for the following two binary endpoints:

- Progression of COVID-19 through Day 29 as defined by hospitalization > 24 hours for acute management of illness due to any cause or death

- Progression of COVID-19 through Day 29 as defined by visit to a hospital emergency room for management of illness or hospitalization for acute management of illness for any duration and for any cause or death

Multiple imputation of endpoint data will be performed to impute data post study withdrawal or intercurrent event, as follows:

- Data will have a monotone missing structure so there will be no intermittent missing data.
- Imputation of missing data will proceed iteratively for each study day starting with Day 2 and ending at Day 29 using a logistic regression imputation model including the analysis model covariates and a parameter for COVID-19 progression status for the previous study day, i.e. imputation of COVID-19 progression status at Day X will include a covariate for status at Day X-1 from the previous imputation step.
- The “likelihood=augment” option in PROC MI will be used in the imputation to avoid quasi complete separation of data for the preceding timepoint covariate included in the imputation model. If logistic regression step fails to converge the following back-up options may be used:
 - i) A discriminant function [Brand, 1999] may be used in place of logistic.
 - ii) MCMC with adaptive rounding.

A sufficient number of imputations will be performed to ensure the stability of the estimates. The results of analysis from each complete imputed dataset will be combined using Rubin’s rule.

Table 3 Multiple Imputation Specifications) details the models, covariates and the seed to be used for the analyses.

Table 3 Multiple Imputation Specifications

Endpoint	Model	Covariates	Post-Baseline Timepoints Included in Prediction Model for Day X (X=2,...,29)	Initial Seed
Proportion of participants who have progression of COVID-19 at Day 29 (hospitalized >24h/death)	Monotone Binary Logistic Regression	Treatment, Age Group at Baseline, Sex	Day X-1	6862

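### A last oxygen record with no end date stays open to database extraction, so a participant who withdrew or was lost can be shown on oxygen on days when nothing was observed

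*SAP*

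**What the plan says.** The oxygen row of SAP 6.2.7 covers a completely missing end date and has two branches. If a later oxygen record with a start date exists, the instruction is to "impute the missing end date as the start date of the subsequent record". If none exists: "If end date is missing and no subsequent record exists, the method of oxygen supplementation will be considered ongoing at time of database extraction". Neither branch refers to death, withdrawal or last contact.

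Oxygen status is used in these places:

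- SAP 4.5.5, a safety section, plans "proportions of participants with change from baseline to higher respiratory support in each category by study day using a stacked bar chart". Its support categories run from room air to mechanical ventilation, with Death as a separate category.
- SAP 4.1.1: "Hospitalization status, oxygen supplementation and healthcare resource utilization use will be slotted against the clinical visit date for summaries and analyses by visit".
- SAP 4.3.1.4 defines the severe or critical respiratory endpoint at Days 8, 15, 22 and 29, and an ordinal scale in which Death is the top tier.

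On missing data in general, SAP 6.2.6 states: "No missing data imputation will be performed for safety endpoints".

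**The concern.** Treating an unclosed record as ongoing is sensible while the participant is still being followed. Once contact has ended, it turns the last known status into an indefinite one. In a chart drawn by study day, a participant who left the study with an open oxygen record looks the same as one seen on oxygen that day. Few participants in this trial are likely to need oxygen, so a single record of this kind can be visible in an arm's bar. The reader of the chart would have no means of telling observed support from assumed support.

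**Working it through.** No figure in the plan depends on this rule, so there is none to reproduce. The check follows an open record through each use of oxygen status, then sizes one record.

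**1. Which records are reached.** Both conditions must hold: the end date is completely missing and no later oxygen record exists. A stop date, or a later record with a start date, closes the episode. The rule therefore touches only a participant's last, unclosed record.

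**2. A participant lost at Day 6 with such a record.**

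- *By-day chart (SAP 4.5.5).* Under 6.2.7 the method is ongoing until extraction. Each study day after Day 6 that the chart shows falls before extraction, so the participant is placed in an oxygen category on all of them. Nothing was observed on those days.
- *By-visit summaries (SAP 4.1.1).* Oxygen is slotted against a visit date. This participant has no Day 8, 15, 22 or 29 visit, so carry-forward into these summaries is not established.
- *Severe or critical endpoint (SAP 4.3.1.4).* The text adds deaths as follows: "Participants who die prior to the timepoint of interest without first having received supplemental oxygen will be considered to have met the endpoint". Singling out those who had no oxygen first implies that earlier oxygen already counts. On that cumulative reading the participant is already an event and carry-forward changes nothing. Only if the endpoint meant status on the named day could an open record matter.
- *Progression endpoints.* The primary endpoint and the secondary progression endpoint are built from emergency visits, hospitalization and death, not oxygen. SAP 6.2.8 gives them their own method: "Multiple imputation will be used to impute data that is missing following withdrawal of the subject from the study". It names only these two endpoints. The other formally tested endpoint is viral-load AUC, which does not use oxygen either.
- *Duration.* Time on a ventilator appears in an exploratory objective (SAP 1.1), and ventilation duration in the study-day convention (6.2.4). SAP 4.4.1 lists no oxygen or ventilation duration summary. For an unchanged record, status through Day 29 is the same in the Day 29 and Week 36 reports.

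**3. A participant who dies with such a record.** Death is a category in 4.5.5 and a tier in 4.3.1.4, so the displays have a place for this participant. What is missing is a statement that Death takes precedence over the open record.

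**4. Whether another rule closes the record.** SAP 4.1.3 gives no rule for respiratory status after withdrawal. The general row of 6.2.7 bars imputed partial dates from duration derivations, but it speaks of partial dates, not wholly missing ones. SAP 6.1.1 does cap follow-up time, at the earliest of withdrawal, data cut and completion, with the death date serving as the withdrawal date for the deceased. That formula is not linked to the oxygen rule.

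**5. Size.** Inputs: 340 per arm planned (SAP 5); progression of 2.7% (500 mg IM) and 1.3% (500 mg IV) (Protocol 1.1).

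- One open record: 1/340 = 0.29 percentage points on each affected day.
- Five open records: 5/340 = 1.47 points.
- For scale, progressors per arm: 0.013 × 340 = 4.4 and 0.027 × 340 = 9.2.

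The progressor counts are a rough guide only. Not every progressor needs oxygen, and oxygen used at home also counts (footnote to the ordinal scale in 4.3.1.4), so they do not bound the number on oxygen. The number of open last records is not in the documents and could be zero.

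**The case against.** The strongest reply is that this is a programming detail. SAP 1 sends further data-handling conventions and display specifications to a separate programming document that is not available here, and a cap may be written there. That possibility stands, but 6.2.7 states a positive rule, and a programmer who follows it as written produces the wrong status.

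A reader might infer more than the text supports, in four ways:

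- *That everyone who died or withdrew on oxygen is counted as still on it.* The rule reaches only open last records, and Death has its own category.
- *That the rule contradicts SAP 6.2.6.* The tension is slight. Section 6.2.7 is a specific rule for dates and also imputes partial adverse-event dates, so 6.2.6 evidently does not forbid date conventions. The adverse-event row does leave wholly missing dates unimputed, so the oxygen row is less cautious than its neighbour, but that is not a contradiction.
- *That the results depend on the extraction date.* Only a duration would, and none is planned.
- *That a large share of an arm's oxygen count is at risk.* Any such percentage needs a number of open records and a number of oxygen users, and the documents give neither.

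It can also be said that setting status to missing drops people last seen on oxygen, who may have left because they were unwell, and so may understate later support. That is fair. It is a reason to show the observed denominator; it does not justify displaying assumed use as if it had been seen.

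**Conclusion.** The point holds as a minor one. As written, SAP 6.2.7 gives a participant who withdrew or was lost with an open last oxygen record an unobserved oxygen status on later days of the by-day chart in 4.5.5. For deaths, only the order of precedence is unstated. The effect is 0.29 percentage points per record per day at 340 per arm, with the number of records unknown. It is confined to descriptive respiratory-support displays.

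The conclusion assumes that the programming document adds no cap and that the arms are near their planned size. That the severe or critical endpoint is unaffected rests on reading it as cumulative. The conclusions on the primary and formally tested secondary endpoints do not depend on these assumptions.

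**What to change.** Replace the second branch of the oxygen row in SAP 6.2.7 with a rule to this effect: where the end date is missing and no later record exists, oxygen ends at the earliest of death, study withdrawal, last contact and data cut-off. Add three conventions for the display in 4.5.5:

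- From death onward the participant is counted in Death only.
- After withdrawal or last contact, respiratory status is missing. This should apply to every participant, including those last seen on room air; otherwise only oxygen users would leave the denominator.
- The number with observed status is printed under each day's bar.

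This is the same kind of limit that SAP 6.1.1 already applies to follow-up time. It costs a few lines in the SAP and one programming condition, on dates that are already collected. The downside is that participants last seen on oxygen leave the later-day display; the printed denominator makes that visible.

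The SAP is based on protocol Amendment 3, and Day 29 results of the main study are already reported in the protocol, so any rerun of that chart should be labelled as a later change. Protocol 9.4 foresees a plan to be finalized before Cohort A is reported; if it reuses these conventions, it should carry the amended rule.

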6.2.8. Statistical Modelling - Multiple Imputation

Multiple imputation will be used to impute data that is missing following withdrawal of the subject from the study, or following an intercurrent event for hypothetical estimands (if applicable), for the following two binary endpoints:

- Progression of COVID-19 through Day 29 as defined by hospitalization > 24 hours for acute management of illness due to any cause or death

- Progression of COVID-19 through Day 29 as defined by visit to a hospital emergency room for management of illness or hospitalization for acute management of illness for any duration and for any cause or death

Multiple imputation of endpoint data will be performed to impute data post study withdrawal or intercurrent event, as follows:

- Data will have a monotone missing structure so there will be no intermittent missing data.
- Imputation of missing data will proceed iteratively for each study day starting with Day 2 and ending at Day 29 using a logistic regression imputation model including the analysis model covariates and a parameter for COVID-19 progression status for the previous study day, i.e. imputation of COVID-19 progression status at Day X will include a covariate for status at Day X-1 from the previous imputation step.
- The “likelihood=augment” option in PROC MI will be used in the imputation to avoid quasi complete separation of data for the preceding timepoint covariate included in the imputation model. If logistic regression step fails to converge the following back-up options may be used:
 - i) A discriminant function [Brand, 1999] may be used in place of logistic.
 - ii) MCMC with adaptive rounding.

A sufficient number of imputations will be performed to ensure the stability of the estimates. The results of analysis from each complete imputed dataset will be combined using Rubin’s rule.

Table 3 Multiple Imputation Specifications) details the models, covariates and the seed to be used for the analyses.

Table 3 Multiple Imputation Specifications

Endpoint	Model	Covariates	Post-Baseline Timepoints Included in Prediction Model for Day X (X=2,...,29)	Initial Seed
Proportion of participants who have progression of COVID-19 at Day 29 (hospitalized >24h/death)	Monotone Binary Logistic Regression	Treatment, Age Group at Baseline, Sex	Day X-1	6862
Proportion of participants who have progression of COVID-19 at Day 29 (ER visit/hospitalized/death)	Monotone Binary Logistic Regression	Treatment, Age Group at Baseline, Sex	Day X-1	376

The seeds were generated using the following code:

```
DATA seeds;
DO i=1 to 3;
seed=int(10000*ranuni(214366));
```

```
OUTPUT;  
END;  
RUN;
```

The same seed is used for all estimands and sensitivity analyses. If additional seeds are required, then the initial seed as specified will be incremented by 1.

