1. INTRODUCTION

The purpose of this SAP is to describe the planned analyses to be included in the Clinical Study Report for Study VIR-7831-5008. Details of the final Day 29 efficacy and safety analyses and 36-Week Safety Follow-Up analyses are provided.

Additional detail with regards to data handling conventions and the specification of data displays will be provided in the Output and Programming Specification (OPS) document.

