1.2. Study Design

Overview of Study Design and Key Features	
 
Total N=1020
 
Randomize 1:1:1
 
 Sotrovimab 500mg IV (N=340) Sotrovimab 500mg IM (N=340) Sotrovimab 250mg IM (N=340) 	 
36 Week Follow Up
 
Interim analysis (~50% of participants)

Design Features
 
 • This study is a Phase 3 randomized, multi-center, open label, non-inferiority study of intramuscular (IM) versus intravenous (IV) administration of sotrovimab, a monoclonal antibody (mAb) against SARS-CoV-2 for the treatment of mild/moderate COVID-19 in participants aged 12 years and older at high risk of disease progression. • Approximately 1020 participants will be enrolled and randomized 1:1:1 to receive a single 500 mg IV infusion of sotrovimab, a single 500 mg IM injection of sotrovimab, or a single 250 mg IM injection of sotrovimab. • Participants with early, mild/moderate COVID-19 who are not on supplementary oxygen and are at risk for disease progression will receive an IV infusion or IM injection of sotrovimab. The intravenous sotrovimab dose will be 500 mg and will be infused over 15 minutes. The intramuscular sotrovimab dose will be either 250 mg or 500 mg given at a single timepoint. The 250 mg IM dose will be given either as a single 250 mg (4ml) injection in the dorsogluteal muscle or as two 2ml injections in each deltoid muscle. The 500 mg IM dose will be administered as two 4ml injections in each dorsogluteal muscle. • After IV infusion or IM injection, participants will be monitored for 30 minutes with vital signs assessments performed every 15 minutes. Injection site reaction assessments, for IM arms only, will be performed at 15 and 30 minutes after injection. 	

Overview of Study Design and Key Features	
	
 • All participants will be actively monitored on an outpatient basis with frequent collection of nasopharyngeal swabs for virology and blood draws for PK sampling and safety labs, as well as in-clinic evaluations at Weeks 1, 2, 3, 4, 12, 20 and 24 as detailed in the Schedule of Activities. • Starting at Week 8, participants will be monitored monthly via phone call or in-clinic evaluation to assess for the incidence and severity of subsequent COVID-19 illness, if any, for a total of 36 weeks from dosing.

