4.2.2. Main analytical approach

The primary analysis will be conducted on the ITT analysis set, excluding participants who did not meet key inclusion/exclusion criteria (see section 4.2.2.1). All intercurrent events (see below) will be handled using a hypothetical strategy for the primary estimand, i.e. assuming the intercurrent event had not occurred.

The primary endpoint will be summarized using counts and percentages of the number of participants who have progression of COVID-19. The proportion of participants meeting the primary endpoint will be compared for sotrovimab 500 mg IM vs sotrovimab 500 mg IV using a 3.5% non-inferiority margin on the risk difference scale as per section 2.

The proportion of participants meeting the primary endpoint will be compared between treatments using a generalized linear model (GLM) from the binomial family with identity link, adjusted for treatment group (sotrovimab 500mg IV, sotrovimab 500mg IM), derived age group (<65 years old, ≥65 years old, see Section 6.2.7), and gender (female, male).

The absolute risk difference and associated 95% CI will be computed to test for non-inferiority in hypothesis (1).

Covariates may be removed from the model if it fails to converge as described in section 4.1.1. If the model still does not converge a GLM assuming a normal distribution for the endpoint and with identity link will be used, adjusted for the covariates above. If no events are observed on either treatment arm, the Farrington-Manning test will be used to compare arms.

The anticipated intercurrent events are:

- Not receiving randomized treatment or an alternative study treatment (i.e. treatment misallocation)
- Discontinuation of study intervention as described in Protocol Section 7.1.
- Use of medication not permitted during the study as listed in Protocol Section 6.8.1 up to day 29

Events are only deemed to be intercurrent events if they occur before occurrence of the primary endpoint. Data observed in the period following an intercurrent event (i.e. from the study day following the intercurrent event) will be excluded from the analysis. Data from this period will be assumed “missing at random” (MAR).

For participants that withdraw from the study and do not meet the primary endpoint at the time of withdrawal, data in the post-withdrawal period will also be assumed MAR.

Details of the method for multiple imputation is described in section 6.2.8.

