4.2.3. Additional estimands

A supplementary estimand will be conducted in the ITT analysis set by handling all intercurrent events with a treatment policy strategy (i.e. regardless of the intercurrent events occurring), with all the other attributes being the same as in the primary estimand. To estimate this estimand, all data collected in the population of interest up to Day 29 will be included in the analysis. Missing data due to participant withdrawal from study will be handled in the same manner as the primary estimand.

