4.2.4. Sensitivity analyses

To assess the sensitivity of the results to the missing data, a tipping point analyses will be performed for the hypothetical and treatment policy estimands. The underlying response rate among those subjects with missing response status in each arm will be varied ranging between 0 and 1. This analysis will be two-dimensional, i.e. it will allow for assumptions about the assumed response rate (and thus missing outcomes) in the two treatment arms to vary independently. For combinations of the assumed response rates in the arms, the number of additional responders among subjects with missing response will be imputed multiple times by drawing from a binomial distribution. The absolute difference and associated standard error for each imputed dataset will be calculated using the primary analysis model and results combined using Rubin's rules to calculate the risk difference and the 95% CI for the treatment comparison. Results will be presented via a heatmap.

In addition, a summary of the number of COVID-19 progressions through Day 29 (as defined in section 4.2.1) for the hypothetical estimand will be provided for the split by those progressions that occur <3 days and ≥ 3 days post-dose.

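### The daily multiple-imputation chain for COVID-19 progression imputes far too many events: it costs power if missing data are balanced and biases IM minus IV if they are not

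*SAP*

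**What the plan says.** The primary endpoint is hospitalization for more than 24 hours, or death, through Day 29. SAP 6.2.8 imputes it after withdrawal and, for the hypothetical estimand, after an intercurrent event. It works one study day at a time from Day 2 to Day 29. Each day has its own logistic model with treatment, age group and sex (Table 3) and the previous day's status: "imputation of COVID-19 progression status at Day X will include a covariate for status at Day X-1 from the previous imputation step".

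The section foresees sparse data. The augmented-likelihood option of PROC MI "will be used in the imputation to avoid quasi complete separation of data for the preceding timepoint covariate included in the imputation model". A discriminant function or MCMC with rounding is available only if the logistic step does not converge. The second Table 3 endpoint (emergency visit, any hospitalization or death) uses the same scheme.

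SAP 4.2.2 sets later data to missing after non-receipt of the randomized treatment, misallocation, discontinuation or prohibited medication. Observed progressors are protected: "Events are only deemed to be intercurrent events if they occur before occurrence of the primary endpoint".

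Two other analyses bear on missing data. For the treatment-policy estimand in SAP 4.2.3, "Missing data due to participant withdrawal from study will be handled in the same manner as the primary estimand". In the tipping-point analysis in SAP 4.2.4, "the number of additional responders among subjects with missing response will be imputed multiple times by drawing from a binomial distribution".

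**The concern.** Status through Day X is permanent: a participant who has progressed by Day X-1 has progressed by Day X. The SAP nevertheless treats the previous day's status as an ordinary covariate in 28 separate models. It does not restrict those models to participants still at risk or hold status once progression is reached. Nor does it ask for a comparison of imputed with observed rates. Imputed progressors can therefore revert, but reversion lowers the imputed rate; it is a symptom and not the cause.

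The cause is sparseness. Each daily model sees almost no new events, so the augmentation pseudo-records and the random coefficient draws largely determine the imputed daily risk. A small daily surplus repeated up to 28 times becomes a large one. The missing-at-random assumption is not at fault; the bias arises within it.

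The surplus arises per missing participant. If the arms lose equal fractions, it inflates variance and costs power. If they do not, IM minus IV moves by roughly the surplus rate times the imbalance. SAP 1.2 describes a "Phase 3 randomized, multi-center, open label, non-inferiority study of intramuscular (IM) versus intravenous (IV) administration of sotrovimab", and nothing in the documents shows that missingness is equal by arm. The Protocol Synopsis reports an adjusted difference of 1.11% with an upper limit of 3.45%, which is 0.05 points inside the margin.

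**Working it through.** **Inputs.** From SAP 5: 340 per arm, 2% in each arm, margin 3.5 points, one-sided 2.5%. From SAP 6.2.8: 28 daily models, each with 5 parameters (intercept, treatment, age group, sex, previous-day status). Not in the documents, so assumed: augmentation weight, missing fraction and timing.

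**The plan's own figure.** SE = sqrt(2 x 0.02 x 0.98 / 340) = 1.074 points. 3.5 / 1.074 - 1.96 = 1.30, which gives power of 90.3%. The stated 90% reproduces; it contains no allowance for missing data.

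**Mechanism by hand.**
- New events per daily model: 0.02 x 680 / 28 = 0.49.
- If the total augmentation weight equals the 5 parameters, split equally between outcomes, each model gains 2.5 pseudo-progressions.
- Added daily risk is about 2.5 / 685 = 0.37%. Over 28 days, 1 - (1 - 0.00365)^28 = 9.7%, before any coefficient noise.

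**Simulation.** The code is purpose-written and is not PROC MI. It used 20 imputations, Rubin's rules, an unadjusted risk difference and no covariate effects. Runs numbered 10,000 per power or reported-rate setting, 20,000 per margin setting (10,000 for prevalence weighting) and 5,000 per sensitivity setting. The comparator is one pooled discrete-time hazard model fitted to participants at risk. The base case is weight 5, split equally.

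| Imputed progression, 2% v 2% | SAP chain | Truth | Hazard model |
|---|---|---|---|
| Missing from a uniform day | 7.9-8.1% | 1.0% | 1.3-1.4% |
| Missing from Day 1 | 11.2-11.5% | 1.9-2.0% | 2.5-2.6% |

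Sensitivity at 5% missing: weight 1, 7.5%; weight 10, 12.4%; pseudo-records weighted by outcome prevalence, 18-19%; events clustered early, 8.5% against 0.4% true.

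Separately written code gave about 7-19% against 0.1-2.6% true at weights 1 to 8. It also isolated the sources. With coefficient draws suppressed, early events and data missing from the start (truth 2.6%), weight 5 gave 11.2%, weight 1 gave 3.9% and weight 0.1 gave 2.3%. Pseudo-events and draw noise thus both contribute, and the surplus vanishes when both are removed. More extreme variants went higher: 17.5-31.8% at weight 16, and about 50% with pseudo-records centred on each outcome group's means. I do not rely on these, but they show how far the size depends on implementation.

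**Balanced missingness.** Complete-data power in the simulation is 89%.

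| Missing per arm | SAP chain, uniform / Day 1 | Hazard model, uniform / Day 1 |
|---|---|---|
| 1% | 88.1 / 87.4% | 88.9 / 89.0% |
| 2% | 86.6 / 85.5% | 88.9 / 88.6% |
| 5% | 81.3 / 78.8% | 88.3 / 87.5% |

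Under uniform timing the CI widens by 3.6%, 7.1% and 18%.

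**Unbalanced missingness at the margin** (5.5% v 2.0%; complete-data difference 3.50, false non-inferiority 3.4-3.6%).
- 8% IV, 2% IM: difference 3.06 (uniform) or 2.85 (Day 1); false non-inferiority 3.9-4.0%, against 3.2-3.3% with the hazard model.
- 2% IV, 8% IM: 3.92 or 4.08; 0.6-1.0%.
- 4% IV, 1% IM: 3.29 or 3.19; 3.5-3.7%.
- 8% IV, 2% IM under prevalence weighting: 2.79, but the wider CI cuts false claims to 1.2%.

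Check of the bias rule at 8% IV, 2% IM: (8.6 - 1.4) x 6% = 0.43 against a simulated 0.44 (uniform); 10.4 x 6% = 0.62 against 0.66 (Day 1).

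**Near the reported rates** (2.7% v 1.3%; complete-data mean upper limit 3.48; hazard model 3.50-3.54).

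| Missing IV / IM | Mean upper limit, SAP chain | Trials where the SAP and hazard verdicts differ |
|---|---|---|
| 3% / 3% | 3.70 | 6.7% |
| 2% / 6% | 4.08 | 16.9% |
| 6% / 2% | 3.51 | 3.6% |

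**The case against.** The strongest reply concerns consequence, not mechanism. Near the reported rates, the one tested imbalance that favours IM leaves the mean upper limit at 3.51 against 3.48 with complete data; the other two settings raise it. For the decision limit the method is on average neutral to conservative, and the reported limit already lies inside the margin. False non-inferiority rises only slightly, and the second simulation could not separate that rise from simulation error. This stands: the finding does not show that the non-inferiority claim was helped. The verdict changes also come from rates close to the margin, where small perturbations flip results.

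Missing data may also be few. Protocol 7.1 and 7.2 expect discontinuation and withdrawal to be rare or uncommon, 8.1.3 collects secondary contacts, and 6.8.1 exempts some standard-of-care medication. Those sections come from Amendment 4, whereas SAP 2.0 rests on Amendment 3, which is not supplied. They suggest low missingness, not equal missingness, and at 1-2% balanced the loss is modest.

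The Output and Programming Specification may hold an at-risk rule, since SAP 1 says: "Additional detail with regards to data handling conventions and the specification of data displays will be provided". It is not supplied, so this remains open. A simple absorbing rule there would not be enough (see the fix).

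The tipping-point heatmap bypasses the daily models and can display low imputed rates in both arms. That helps readers but leaves the primary estimate and CI as they are.

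Finally, the comparator was tested without covariate effects and with an unadjusted risk difference, and no hazard-model result is available for early-clustered events. These limits stand.

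**Conclusion.** The concern holds. As written, the chain over-imputes progression: 7.5-19% against 0.4-2% true in the main simulations, with the same direction at every augmentation weight tried from 1 to 8 with coefficient draws included. With balanced missingness the cost is power, about 2-4 points at 2% missing and 8-10 points at 5%. With 8% against 2% missing, the difference is biased by about 0.4-0.7 points, downward if IV loses more data and upward if IM does. Inflation of false non-inferiority is small.

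All sizes depend on assumed weights, missing fractions and timing, and none come from PROC MI itself. At 2% missing or less the effect on the difference is small. The direction in this trial cannot be known without missing counts by arm. The reported CI is not evidence of the error: its half-width of 2.345, against 2.10 for a simple binomial at 340 per arm, could reflect covariate adjustment or actual arm sizes.

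**What to change.** For both Table 3 endpoints, replace the 28 models with one pooled discrete-time hazard model: logistic, with treatment, age group, sex and study week, and a weak prior on the slopes for sparse cells. Fit it to person-days of participants still at risk, impute only those participants, and hold status at 1 once progressed. Making the existing chain absorbing is not enough; in simulation that raised the imputed rate to 11.8% against 1.1% true.

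Report by arm the number with missing status, the reasons, and the imputed rate beside the observed rate. If few are missing, that table settles the matter. Because the Day 29 result is already reported, present the hazard-based imputation as a labelled sensitivity analysis beside the prespecified primary analysis, not in its place.

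The cost is a revised imputation macro, a short SAP addendum and one table. No new data are needed.
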